6.7 LEE011 DOSE MODIFICATION GUIDELINE- PHASE IB CYCLE 2+ AND PHASE II COMPONENTS

Management of severe or intolerable adverse reactions requires temporary dose reduction and/or interruption of LEE011 therapy. Refer to Table 6.3 for guidance. Dose increases once LEE011 has been reduced are not allowed.

Table 6.3 Dose Modification Guidelines

Dose Level	LEE011	
	Dose	Number of capsules & strength
Highest dose (0)	600 mg	3 x 200 mg capsules
First dose reduction (-1)	400 mg	2 x 200 mg capsules
Second dose reduction (-2)	200 mg	1 x 200 mg capsules
Third dose reduction (-3)	Discontinue Treatment of LEE011	

Recommendations for dose reduction, interruption, of discontinuation of LEE011 in the management of adverse reactions are summarized in Table 6-4, Table 6-5, Table 6-6, and Table 6-7. Clinical judgment and discretion of the treating physician should guide the management plan of each patient based on individual benefit and risk assessment.

**Table 6-4 LEE011 Dose Adjustment and Management Recommendations for
HEMATOLOGICAL ADVERSE REACTIONS**

THROMBOCYTOPENIA	
Toxicity/Grade	Dose Adjustment and Management Recommendations
Grade 1 ($\geq 75 \times 10^9/L$)	No dose adjustment required.
Grade 2 ($\geq 50 \times 10^9/L - <75 \times 10^9/L$)	No dose adjustment required.
Grade 3 ($\geq 25 \times 10^9/L - <50 \times 10^9/L$)	Dose interruption until recovery to grade ≤ 2 . Re-initiate LEE011 at the same dose level. If toxicity recurs at grade 3: discontinue LEE011
Grade 4 ($<25 \times 10^9/L$)	Discontinue LEE011.

Toxicity/Grade	Dose Adjustment and Management Recommendations
Absolute neutrophil count (ANC)	
Grade 1 ($\geq 1.5 \times 10^9/L$)	No dose adjustment required.
Grade 2 ($\geq 1.0 - < 1.5 \times 10^9/L$)	No dose adjustment required.
Grade 3 ($\geq 0.5 - < 1.0 \times 10^9/L$)	Dose interruption until recovery to $\geq 1.0 \times 10^9/L$. Re-initiate LEE011 at the same dose level. 
 If toxicity recurs at grade 3: temporary dose interruption until recovery to $\geq 1.0 \times 10^9/L$ and reduce LEE011 dose to the next lower dose level.
Grade 4 ($< 0.5 \times 10^9/L$)	Dose interruption until recovery to $\geq 1.0 \times 10^9/L$. Re-initiate LEE011 at the next lower dose level. 
 If toxicity recurs at grade 4: temporary dose interruption until recovery to $\geq 1.0 \times 10^9/L$ and reduce LEE011 at the next lower dose level.
Febrile Neutropenia	
Grade 3 ANC $< 1.0 \times 10^9/L$ with [a single temperature of $> 38.3^\circ C$ ($101^\circ F$) or a sustained temperature of $\geq 38^\circ C$ ($100.4^\circ F$) for more than one hour]	Dose interruption until improvement of ANC $\geq 1.0 \times 10^9/L$ and no fever. Restart at the next lower dose level. 
 If febrile neutropenia recurs, discontinue LEE011.
Grade 4 Life-threatening consequences; urgent intervention indicated	Discontinue LEE011.
Anemia (Hemoglobin)	
Grade 1 (≥ 10.0 g/dL)	No dose adjustment required.
Grade 2 ($\geq 8.0 - < 10.0$ g/dL)	No dose adjustment required.
Grade 3 (< 8.0 g/dL)	Dose interruption until recovery to grade ≤ 2 . Re-initiate LEE011 at the same dose.

Grade 4 Life-threatening consequences; urgent intervention indicated	Discontinue LEE011.
---	---------------------

**Table 6-5 LEE011 Dose Adjustment and Management Recommendations for
HEPATIC ADVERSE REACTIONS**

HEPATOTOXICITY (BILIRUBIN, ALT, AST)	
TOTAL BILIRUBIN without ALT/AST increase above baseline value	
Grade	Dose Adjustment and Management Recommendations
Same grade as baseline or increase from baseline grade 0 to grade 1	Maintain dose level with LFTs monitored every other-week
Increase from baseline grade 0 or 1 to grade 2 (1.5-3.0 x ULN) or from baseline grade 2 to grade 3 (>3.0 -10 x ULN)	Dose interruption of LEE011 If resolved to \leq grade 1 in \leq 21 days, then maintain dose level If resolved to \leq grade 1 in $>$ 21 days or toxicity recurs, discontinue LEE011

Increase from baseline grade 0 or 1 to grade 3 (>3.0-10 xULN)	Discontinue LEE011
Grade 4 (> 10.0 x ULN)	Discontinue LEE011

Confounding factors and/or alternative causes for increase of total bilirubin should be excluded before dose interruption/reduction. They include but are not limited to: evidence of obstruction, such as elevated ALP and GGT typical of gall bladder or bile duct disease, hyperbilirubinemia due to the indirect component only (i.e. direct bilirubin component ≤ 1 x ULN) due to hemolysis or Gilbert Syndrome, pharmacologic treatment, viral hepatitis, alcoholic or autoimmune hepatitis, other hepatotoxic drugs.
 
For patients with Gilbert Syndrome, these dose modifications apply to changes in direct bilirubin only. Bilirubin will be fractionated if elevated.
	
HEPATOTOXICITY (BILIRUBIN, ALT, AST)	
AST or ALT without bilirubin elevation > 2 x ULN	
AST or ALT Toxicity/Grade	Dose Adjustment and Management Recommendations
Same grade as baseline or increase from baseline grade 0 to grade 1 (confirmed 48 to 72 hrs later)	No dose adjustment required with LFTs monitored per protocol if same grade as baseline or bi-weekly in case of increase from baseline grade 0 to 1

Increase from baseline grade 0 or 1 to grade 2 ($> 3.0 - 5.0 \times \text{ULN}$) or from baseline grade 2 to grade 3 ($> 5.0 - 20.0 \times \text{ULN}$)
	
Dose interruption of LEE011
 
If resolved to \leq baseline value in ≤ 21 days, then maintain dose level
 
If resolved to \leq baseline value in > 21 days or toxicity recurs, discontinue LEE011

Increase from baseline grade 0 or 1 to grade 3 ($> 5.0 - 20.0 \times \text{ULN}$)
	
Discontinue LEE011

Grade 4 ($> 20.0 \times \text{ULN}$)
	
Discontinue LEE011

AST or ALT and concurrent Bilirubin
	

AST or ALT \geq grade 2 ($> 3 \times \text{ULN}$) in patients with normal values at baseline and total bilirubin $> 2 \times \text{ULN}$ o r AST or ALT \geq grade 3 ($> 5 \times \text{ULN}$) in patients with grade 1 or 2 at baseline, and total bilirubin $> 2 \times \text{ULN}$
	
Discontinue LEE011

Confounding factors and/or alternative causes for increased transaminases should be excluded before dose interruption/reduction. They include but are not limited to: concomitant medications, herbal preparations or dietary supplements, infection, hepato-biliary disorder or obstruction, new or progressive liver metastasis, and alcohol intake.
	

Table 6-6 LEE011 dose modification guidance in case of QT PROLONGATION

The ECG are done based on scheduled assessment as detailed in table 7.1.

QTC	
Grade	Dose Modification
For all grades	
 • Check the quality of the ECG • Perform analysis of serum electrolytes (K+, Ca++, Phos, Mg++). If below the lower limit of normal, interrupt LEE011 administration, correct with supplements or appropriate therapy as soon as possible, and repeat electrolytes until documented as normal • Review concomitant medication usage for the potential to inhibit CYP3A4 and/or to prolong the QT interval • Check compliance with correct dose and administration of LEE011
1 QTc 450-480 ms	No dose adjustment required.
2 QTc 481-500 ms	
Interrupt LEE011
 
Perform a repeat ECG one hour after the first QTcF of ≥ 481ms
 
If QTcF < 481 ms, restart LEE011 at the same dose. No dose adjustment for the first occurrence
 
If QTcF remains ≥ 481 ms, restart LEE011 at the same dose level. No dose adjustments required for the first occurrence
 
If QTcF ≥ 481 ms recurs, discontinue LEE011
 
Repeat ECGs 7 days and 14 days after dose resumption (then as clinically indicated) for any patient who has therapy interrupted due to QTcF ≥ 481 ms

3 QTc ≥ 501 ms on at least two separate ECGs	
Interrupt LEE011
 
 • Consider consulting a local cardiologist • Perform a repeat ECG one hour after the first QTcF of ≥ 501 ms • If QTcF remains ≥ 501 ms, repeat ECG as clinically indicated, but at least once a day until the QTcF returns to < 481 ms.

	
 If QTcF returns to < 481 ms, LEE011 should be reduced by 1 dose level. (please refer to the dosing schedule table) 
Repeat ECGs 7 days and 14 days after dose resumption for any patient who has therapy interrupted due to QTcF \geq501 ms
 
 If QTcF of \geq 501 ms recurs, discontinue LEE011

4 QT/QTc \geq 501 or $>$ 60 ms change from baseline
 
And
 
Torsades de pointes or polymorphic ventricular tachycardia, or signs/symptoms of serious arrhythmia
	Discontinue LEE011

Table 6-7 LEE011 Dose Adjustment and Management Recommendations for ALL OTHER ADVERSE REACTIONS

Grade	Dose Adjustment and Management Recommendations
1	No dose adjustment recommended. Initiate appropriate medical therapy and monitor.
2	
Dose interruption until recovery to grade \leq1. Initiate appropriate medical therapy and monitor.
 
Re-initiate LEE011 at the same dose.
 
 If the same toxicity recurs at grade 2, interrupt LEE011 until recovery to grade \leq1. Re-initiate LEE011 at the next lower dose level.

3	
Dose interruption until recovery to grade ≤ 1. Initiate appropriate medical therapy and monitor.
 
Re-initiate LEE011 at the next lower dose level.
 
 • If toxicity recurs at grade 2: temporary dose interruption until recovery to grade ≤ 1 and reduce LEE011 dose the next lower dose level. • If toxicity recurs at grade 3, discontinue LEE011.
4	Discontinue LEE011 and treat with appropriate medical therapy.

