- When up to 3 additional patients are added to a given dose level, if 0-1 of 6 patients has a DLT then the dose will be increased to the next dose level.
- Additional dose levels may be explored per investigator discretion to define the safety profile of the treatment.

The recommended Phase II dose (RP2D) will be the highest cohort level in which one or fewer subjects of 6 develops a first cycle DLT.

The Data and Safety Monitoring Committee as described below will regularly review all serious adverse events and any local adverse events, which are unanticipated problems. The study will utilize the Common Terminology Criteria for Adverse Events (CTCAE) version 4.03 for grading of all adverse events related to treatment.

Table 6.2: Dose-limiting toxicity: phase Ib component

The following will be considered a DLT if they occur within the first cycle of therapy with LEE011 and are determined to be possibly, probably or definitely related to LEE011

Grade 4 neutropenia lasting more than 7 consecutive days
Grade 3 or 4 febrile neutropenia
≥ Grade 3 vomiting ≥ 48 hours despite optimal anti-emetic therapy
≥ Grade 3 diarrhea ≥ 48 hours despite optimal anti-diarrhea therapy
Clinical signs of cardiac disease, such as unstable angina or myocardial infarction, or Troponin ≥ grade 3
Grade 4 serum alkaline phosphatase > 7 days
≥ Grade 3 serum creatinine
≥ Grade 3 adverse event for any non-hematologic toxicity unless otherwise specified as below (excluding alopecia, fatigue < 5 days, laboratory abnormalities that are responsive to oral supplementation or deemed by the investigator to be clinically insignificant).

THROMBOCYTOPENIA	
Toxicity/Grade	Dose Limiting Toxicity and Management Recommendations
Grade 3 ($\geq 25 \times 10^9/L$ - $<50 \times 10^9/L$) without clinically significant bleeding	Dose interruption until recovery to grade ≤ 2 . Re-initiate LEE011 at the same dose level. • If toxicity recurs at grade 3: dose limiting toxicity
Grade 3 ($\geq 25 \times 10^9/L$ - $<50 \times 10^9/L$) with clinically significant bleeding	Dose limiting toxicity
Grade 4 ($<25 \times 10^9/L$)	Dose limiting toxicity

HEPATOTOXICITY (BILIRUBIN, ALT, AST)	
TOTAL BILIRUBIN without ALT/AST increase above baseline value	
Toxicity/Grade	Dose Limiting Toxicity and Management Recommendations
Same grade as baseline or increase from baseline grade 0 to grade 1	Maintain dose level with LFTs monitored every other-week

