Increase from baseline grade 0 or 1 to grade 2 ($1.5-3.0 \times$ ULN) or from baseline grade 2 to grade 3 ($>3.0 -10 \times$ ULN)	Dose interruption of LEE011 If resolved to \leq grade 1 in ≤ 21 days, then maintain dose level If resolved to \leq grade 1 in > 21 days or toxicity recurs, then dose limiting toxicity
Increase from baseline grade 0 or 1 to grade 3 ($>3.0-10$ xULN)	Dose limiting toxicity
Grade 4 ($> 10.0 \times$ ULN)	Dose limiting toxicity

Confounding factors and/or alternative causes for increase of total bilirubin should be excluded before dose interruption/reduction. They include but are not limited to: evidence of obstruction, such as elevated ALP and GGT typical of gall bladder or bile duct disease, hyperbilirubinemia due to the indirect component only (i.e. direct bilirubin component $\leq 1 \times$ ULN) due to hemolysis or Gilbert Syndrome, pharmacologic treatment, viral hepatitis, alcoholic or autoimmune hepatitis, other hepatotoxic drugs.

For patients with Gilbert Syndrome, these dose modifications apply to changes in direct bilirubin only. Bilirubin will be fractionated if elevated.

HEPATOTOXICITY (BILIRUBIN, ALT, AST)

AST or ALT without bilirubin elevation $> 2 \times$ ULN

AST or ALT Toxicity/Grade	Dose Limiting Toxicity and Management Recommendations
Same grade as baseline or increase from baseline grade 0 to grade 1 (confirmed 48 to 72 hrs later)	No dose adjustment required with LFTs monitored per protocol if same grade as baseline or bi-weekly in case of increase from baseline grade 0 to 1
Increase from baseline grade 0 or 1 to grade 2 ($> 3.0 - 5.0 \times$ ULN) or from baseline grade 2 to grade 3 ($> 5.0 - 20.0 \times$ ULN)	Dose interruption of LEE011 If resolved to \leq baseline value in ≤ 21 days, then maintain dose level If resolved to \leq baseline value in > 21 days or toxicity recurs, then dose limiting toxicity
Increase from baseline grade 0 or 1 to grade 3 ($> 5.0 - 20.0 \times$ ULN)	Dose limiting toxicity
Grade 4 ($> 20.0 \times$ ULN)	Dose limiting toxicity

AST or ALT and concurrent Bilirubin	
AST or ALT \geq grade 2 ($> 3 \times$ ULN) in patients with normal values at baseline and total bilirubin $> 2 \times$ ULN or AST or ALT \geq grade 3 ($> 5 \times$ ULN) in patients with grade	Dose limiting toxicity

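### With normal or grade 1 baseline bilirubin, a small AST/ALT rise switches off the bilirubin rules, so some bilirubin rises are handled more mildly than the same rise alone

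*Combined protocol and SAP*

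**What the plan says.** Two tables govern hepatic toxicity. Table 6.2 in section 6.6 ("Dose-limiting toxicity: phase Ib component") covers the first cycle. Table 6-5 falls under the section headed "LEE011 DOSE MODIFICATION GUIDELINE- PHASE IB CYCLE 2+ AND PHASE II COMPONENTS" and covers everything after that. Both split the hepatic rules into three blocks.

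- **Bilirubin rows**, headed "TOTAL BILIRUBIN without ALT/AST increase above baseline value". From baseline grade 0 or 1, a rise to 1.5-3 x ULN means interruption. In Table 6.2, if resolution takes more than "21 days or toxicity recurs, then dose limiting toxicity"; in Table 6-5 the same events mean stopping LEE011. A rise to 3-10 x ULN or beyond is an immediate DLT (Table 6.2) or permanent stop (Table 6-5).
- **AST/ALT rows**, which apply only if bilirubin is not above 2 x ULN. A rise within the baseline grade, or from grade 0 to 1, needs no dose change.
- **Concurrent row**, which needs bilirubin above 2 x ULN plus AST/ALT above 3 x ULN "in patients with normal values at baseline and total bilirubin", or above 5 x ULN for baseline grade 1-2.

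There are two fallbacks. Table 6.2 has a general row that makes a DLT of a "Grade 3 adverse event for any non-hematologic toxicity unless otherwise specified as below" (and of higher grades), with some laboratory exclusions. Table 6-7, for all other reactions, applies from phase Ib cycle 2 and in phase II: grade 2 is interrupted and resumed at the same dose, grade 3 is interrupted and resumed one level lower, and grade 4 stops. In Table 6.3 the step below 200 mg is "Discontinue Treatment of LEE011".

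**The concern.** The three blocks look exhaustive but are not. The bilirubin heading tests the AST/ALT value, not its grade, so any rise above baseline disables those rows. The concurrent row takes over only at a much higher AST/ALT level. A patient whose bilirubin and AST/ALT both rise can therefore be handled more mildly than a patient whose bilirubin alone rises by the same amount.

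At stake is continued or resumed dosing in Child-Pugh A or B7 patients. Sections 9.1 and 9.2 list hepatocellular injury for both LEE011 and chemoembolization, so joint rises are foreseeable.

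**Working it through.** No figure in the plan needs reproducing; the check is an enumeration of the printed rules.

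**Inputs.** Baseline bilirubin grade 0-1. Bilirubin bands of 1.5-2, 2-3, 3-10 and >10 x ULN, from the cut-offs in the tables. Entry requires AST/ALT below 5 x ULN (5.1.10.4), so baseline AST/ALT is grade 0, 1 or 2. Patterns above baseline value: from grade 0 to 0-4 (5), from grade 1 to 1-4 (4), from grade 2 to 2-4 (3), in all 5 + 4 + 3 = 12. Grid: 12 x 4 = 48 cells.

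**Assumptions.** AST/ALT grade 1 starts above ULN. The cut end of the Table 6.2 concurrent row matches Table 6-5. Table 6-7 catches any bilirubin rise that the bilirubin rows miss.

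**Sub-threshold patterns** (above baseline value, below the concurrent row), as baseline-to-new grade: 0-0, 0-1, 1-1, 1-2, 2-2, five in all.

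**First action:**

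| Bilirubin, x ULN | Cycle 1, alone | Cycle 1, sub-threshold AST/ALT rise | Later, alone | Later, sub-threshold AST/ALT rise |
|---|---|---|---|---|
| 1.5-2 | interrupt | no change (interrupt for 1-2) | interrupt | interrupt (Table 6-7) |
| 2-3 | interrupt | no row applies | interrupt | interrupt (Table 6-7) |
| 3-10 | DLT | DLT (general row) | stop | interrupt, one level lower; stop at 200 mg |
| >10 | DLT | DLT (general row) | stop | stop (Table 6-7) |

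**Counts of milder first action**

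- Table 6.2: 4 cells at 1.5-2 (0-0, 0-1, 1-1, 2-2) + 5 at 2-3 = 9 of 48. Varying the baseline grades that the cut words could name gives 9 each time.
- Table 6-5 with Table 6-7: 5 of 48 at 400 or 600 mg, all at 3-10 x ULN; 0 of 48 at 200 mg.
- Baseline bilirubin grade 2: 0 of 48 in both periods.

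**Example.** A phase II patient on 600 mg has bilirubin 0.9 and AST 2 x ULN at baseline. Bilirubin of 5 x ULN with AST unchanged stops LEE011. The same bilirubin with AST at 2.5 x ULN meets no hepatic row, and Table 6-7 lets the patient resume at 400 mg.

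**Later steps.** In 9 further Table 6-5 cells (4 at 1.5-2, 5 at 2-3) the first action is the same but later steps are milder. If the grade 2 recurrence rule of Table 6-7 repeats (assumption), stopping comes at episode 4 (600 mg), 3 (400 mg) or 2 (200 mg), against episode 2 under the bilirubin row. For slow resolution the limit moves from 21 days to the 4 weeks of section 6.5.

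**Post-TACE rule** (section 6.12, LEE011 administration with chemoembolization). AST/ALT must return to baseline grade before LEE011 is started or continued. This can reach cells where AST/ALT has left its baseline grade:

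- Table 6.2: 0-1 at 1.5-2, and 0-1 and 1-2 at 2-3, so 3 of 9; 9 - 3 = 6 remain.
- Table 6-5: 0-1 and 1-2 at 3-10, so 2 of 5; 5 - 2 = 3 remain. Counting these two as covered is generous, since a hold is not a permanent stop.

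The cells left are 0-0, 1-1 and 2-2. At the start of LEE011 the same section also requires bilirubin below 2 x ULN, so only 3 of the 9 (1.5-2 x ULN, AST/ALT within grade) and none of the 5 can arise then. That bilirubin hold is worded for initiation only.

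**The case against.** The case on the other side is about size. The tables give recommendations, alternative causes are to be excluded before acting, and section 6.7 says "Clinical judgment and discretion of the treating physician should guide the management plan of each patient". Section 6.5 also allows treatment to end for unacceptable toxicity or at the investigator's discretion. The post-TACE rule already reaches some cells. In the 1.5-2 x ULN band, entry accepts bilirubin up to 2.0 x ULN and LEE011 may start below that level.

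Most of this stands as a limit on size. The 1.5-2 x ULN cells are of little consequence, and the post-TACE rule narrows the firm gap to within-grade AST/ALT movement. Discretion does not close the gap. The clause sits in section 6.7, outside cycle 1, and it permits a stricter action without supplying the missing rule.

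A reader might infer three stronger things that the documents do not support:

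- *That DLTs are broadly missed and the MTD is biased.* Bilirubin above 3 x ULN remains a DLT through the general row, subject to its exclusions. The DLT routes lost need recurrence, or resolution beyond 21 days, within a 28-day cycle and among 9-18 patients.
- *That 19 of 48 later cells lack a bilirubin action or have a milder one.* This count requires Table 6-7 not to reach bilirubin at all. The documents do not settle that, and I do not rely on it.
- *That deleting the limiting headings is a safe repair.* For baseline bilirubin grade 2 rising to grade 3 with a small AST/ALT rise, it would replace the Table 6-7 dose reduction by resumption at the same dose if resolved within 21 days. It could also turn the general-row DLT into an interruption.

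**Conclusion.** The gap is real and bounded. For baseline bilirubin grade 0-1, a sub-threshold AST/ALT rise gives a milder first action in 9 of 48 cells in phase Ib cycle 1, and in 5 of 48 at 400 or 600 mg afterwards. Allowing for the post-TACE hold, 6 and 3 cells remain firm, all with AST/ALT moving within its baseline grade. The cells that matter are 2-3 x ULN in cycle 1 (3 cells, no row applies) and 3-10 x ULN later (3 cells, stop becomes interrupt and reduce).

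Bilirubin above 10 x ULN, the 200 mg first action and baseline bilirubin grade 2 are unaffected. The cycle 1 count is robust to the cut table row; the later count depends on Table 6-7 reaching bilirubin. Cells are not patients, and the documents give no frequency. The effect on the MTD is small; the point is a safety-action rule that should be corrected.

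**What to change.** Add one rule to Tables 6.2 and 6-5: if AST/ALT is above its baseline value and the concurrent row is not met, apply the action listed for the bilirubin change as if AST/ALT had not risen, or any other action that already applies (AST/ALT row, Table 6.2 general grade 3 or higher row, Table 6-7), whichever is stricter.

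State that the general row and Table 6-7 stay in force for these patients. Baseline bilirubin grade 2 rising to grade 3 with an AST/ALT rise is then handled no more mildly than now. Leave the printed bilirubin rows unchanged where AST/ALT has not risen.

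The cost is one amendment and no new tests. The downside is a few more interruptions or discontinuations and, rarely, an extra first-cycle DLT. That last matters most in cohort 1, where two end the phase I part with no phase II.

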6.5 TREATMENT DURATION

Patients will receive trial treatment until one of the following criteria applies:

- disease progression,
- unacceptable toxicity or toxicity that results in treatment interruption of >4 weeks,
- patient experiences DLT

- patient decides to withdraw from study, starts a new therapy or is lost to follow up
- discontinuation from the study treatment for any other reason.
- PI or study sponsor discretion

Patients who come off therapy will be followed for survival regardless of cause of treatment discontinuation.”

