6.6 DOSE LIMITING TOXICITIES-PHASE IB COMPONENT

The phase Ib component of the study will consist of 3+3 dose escalation rule with the dose of LEE011 escalating up to 600mg daily to determine the maximum tolerated dose (MTD) that will be used during the phase II component. The dose levels for the phase Ib aspect will be 200 mg, 400 mg, or 600 mg daily.

Only the first cycle of therapy (one cycle equals to one month) will be used to determine dose limiting toxicity (DLT). However, if two total grade 5 adverse events or 2 Grade 4 adverse events (lasting ≥ 7 days); occur at any time while the patient is still receiving study treatment that are either: definitely, probably, or possibly related to either LEE011 or TACE the study will be terminated to enrollment.

Only patients started on the first dose of LEE011 will be included in the evaluation of DLT. If a patient has a DLT that patient will not receive further LEE011. Patients following initial chemoembolization who never receive LEE011 will not be included in the MTD analysis and will be replaced. The patients will be followed for thirty days following the initial chemoembolization for safety assessment. Patients will be enrolled into the next highest drug cohort only after 3 or 6 patients have completed the first cycle of therapy. Once the MTD is determined, patients at the MTD dose will continue with LEE011 and represent the first three patients accrued to the phase II aspect.

Due to observed (TACE related, non DLT) toxicity on cohort 1 specific criteria for cohort 1 has been developed after discussion with the FDA. Cohort 1 has been expanded to 6 patients. Decision for dose escalation will be made using the following criteria:

- No or one DLT: the next three patients will be assigned to next higher dose level (400 mg of LEE011).
- At least two toxicities: the MTD is exceeded and the phase I component of the trial will be stopped with no continuation into the phase II component.

For Cohort 2 and 3 the following traditional 3+3 dose escalation rules will be used:

- If a dose limiting toxicity (DLT) is observed in 1 out of 3 patients at a given dose level, up to 3 additional patients will be enrolled and treated at that dose level.
- If 2 out of 3-6 patients at that dose level have DLTs, the dose will be decreased to the previous dose level, and up to 3 additional patients will be enrolled at that dose level for a total of 6 patients.

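### The grade 2 QTc row restarts LEE011 at the same dose even when the one-hour repeat QTcF is still 481 ms or more

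*Combined protocol and SAP*

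**What the plan says.** The grade 2 QTc row appears twice: in Table 6.2 (section 6.6), which governs cycle 1 of phase Ib, and in Table 6-6 (section 6.7), which governs later phase Ib cycles and phase II. Both say to interrupt LEE011 and take a second ECG one hour after the first QTcF of 481 ms or more. Two branches follow:

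- QTcF now below 481 ms: restart at the same dose.
- QTcF still 481 ms or more: "restart LEE011 at the same dose level. No dose adjustments required for the first occurrence".

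If a value of 481 ms or more recurs, it is a DLT under Table 6.2 and leads to discontinuation under Table 6-6. Further monitoring is set by "Repeat ECGs 7 days and 14 days after dose resumption (then as clinically indicated").

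The grade 3 QTc row is different. If the value stays at 501 ms or more, the ECG is repeated "at least once a day until the QTcF returns to" below 481 ms, and LEE011 then resumes one dose level lower.

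For cohort decisions, section 6.6 states: "Only the first cycle of therapy (one cycle equals to one month) will be used to determine dose limiting toxicity (DLT"). It adds: "If a patient has a DLT that patient will not receive further LEE011". Section 6.5 ends treatment for "unacceptable toxicity or toxicity that results in treatment interruption of" more than 4 weeks.

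**The concern.** The one-hour ECG separates patients whose QTcF has recovered from those whose QTcF has not, and the row then treats both groups alike. Followed as written, a patient whose QTcF has not come down goes back on the dose at which the prolongation appeared.

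The plan itself treats QT as a real risk for this drug. Section 1.7.3 reports QT and QTc prolongation in dogs, with potential for premature ventricular contractions at higher exposure. Section 1.7.4 gives lower QTcF risk as one reason for preferring 600 mg to the 900 mg MTD.

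The second issue is the word *recurs*. Suppose a patient never fell below 481 ms and is still there at the 7-day ECG. That value could be a new occurrence, or the first one continuing. In cycle 1 the first reading makes a DLT and the second does not. A single classification could move a cohort from 0/3 to 1/3 or from 1/6 to 2/6. In cohort 1, two events mean that "the MTD is exceeded and the phase I component of the trial will be stopped", with no phase II.

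**Working it through.** The plan gives no figure to reproduce, so the main check sets the restart conditions side by side.

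| Table and row | Condition for restarting LEE011 |
|---|---|
| 6-4, platelets grade 3 | recovery to grade 2 or better |
| 6-4, neutrophils grades 3 and 4 | ANC at least 1.0 × 10⁹/L |
| 6-4, febrile neutropenia grade 3 | ANC at least 1.0 × 10⁹/L and no fever |
| 6-4, hemoglobin grade 3 | recovery to grade 2 or better |
| 6-5, bilirubin | grade 1 or better within 21 days |
| 6-5, AST or ALT | baseline value or better within 21 days |
| 6-6, QTc grade 3 | QTcF below 481 ms, then one dose level lower |
| 6-7, other reactions grades 2 and 3 | recovery to grade 1 or better |
| **6-6, QTc grade 2** | **none** |

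Table 6.2 shows the same pattern: its bilirubin and AST/ALT rows require resolution within "21 days, then maintain dose level", while its grade 2 QTc row requires none.

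**Do the checks for all QTc grades fill the gap?** They require an ECG quality check, serum electrolytes (with interruption and correction if low), a review of concomitant drugs, and a compliance check. None sets a QTcF value for restart.

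**Does the one-hour interruption lower exposure?** Inputs from section 1.7.4.1: effective half-life 32.6 h, steady state by about day 8. Fraction eliminated in one hour = 1 − 2^(−1/32.6) = 0.021, about 2%. Dosing is once daily, and section 6.4 treats a dose as missed only if it is more than 6 hours late. If restart follows directly on the repeat ECG, no dose need be missed. The row does not say when restart happens, so this is conditional.

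**When is the next look?** Seven days after resumption. For illustration, same-day restart at an on-schedule Day 15 visit puts that ECG on Day 15 + 7 = 22, after the seven doses of Days 15-21.

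**How common is it?** Section 1.7.4, Table 2-2, at 600 mg: QT prolongation in 10 of 67 patients at any grade and 0 of 67 at grade 3/4. All ten cases were therefore grade 1 or 2, and grade 2 lies between 0/67 = 0% and 10/67 = 15%. The share still at 481 ms or more after one hour is not given. If the 600 mg rate carried over, and every case were grade 2 and persistent, 40 phase II patients would yield 40 × 10/67 = 6.0. That is a ceiling under those assumptions, not an estimate, and the floor is zero. The documents give no QT rates for 200 or 400 mg.

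**The case against.** The best defense is that this is a deliberate one-strike rule: one same-dose continuation at 481-500 ms, then permanent discontinuation. On a second event that is stricter than Table 6-7, which reduces the dose when a grade 2 reaction recurs. The one-hour ECG can still reveal a rise to 501 ms or more. Patients with QTcF above 450 ms are excluded at entry. Section 6.7 leaves room for the treating physician's judgment, and section 16.0 provides real-time toxicity review during escalation.

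These points lower the risk, but none supplies a recovery threshold. The discretion clause stands in section 6.7, not in the DLT rules of section 6.6, and section 17.0 asks for conduct as the protocol describes. The real-time toxicity review is specified for the dose-escalation phase.

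On *recurs*, the objection largely succeeds. The row runs in sequence from first occurrence to recurrence to the 7- and 14-day ECGs, so the likelier reading is that a value of 481 ms or more at those ECGs is a recurrence. One clause would settle it.

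Three stronger inferences are tempting, and the documents do not support them:

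- *The 7-day ECG always falls inside the DLT window.* This needs restart on or near the Day 15 visit. Restart timing is not stated, and an electrolyte hold running past Day 21 would move restart into cycle 2. Whether the ±3 day visit window (section 7.1, note 4) applies to the 7-day ECG is also unclear, so the number of doses before it is not fixed.
- *The gap has a calculable chance of altering an escalation decision.* That also needs persistence at one hour and at the later ECG, attribution to LEE011, and a cohort already at its threshold. None of these has a rate in the documents. Cohort 1 receives 200 mg, for which no QT rate is given.
- *Grade 2 needs its own recovery deadline in cycle 1.* The grade 3 QTc row has none, so a grade 2 deadline would make the milder event the stricter one.

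**Conclusion.** The main point holds on the text alone. In both tables the two grade 2 branches lead to the same dose, and this is the only interruption row in Tables 6-4 to 6-7 that does not wait for recovery. It may be a drafting slip, but the documents do not say so. The undefined recurrence is a real but secondary gap with a likelier reading.

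The size is unknown. Grade 2 frequency at 600 mg is bounded between 0 and 15%, assuming that the first-in-human patients are informative for this population; persistence is unreported, and the effect on escalation cannot be quantified. The case for change rests on the safety logic and the small cost of correction, not on an expected count. The change should be made.

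**What to change.** In the grade 2 QTc row of Tables 6.2 and 6-6, replace the second branch. If QTcF remains at 481 ms or more, hold LEE011 and repeat the ECG at least once a day until it is below 481 ms, then restart at the same dose. Add that any QTcF of 481 ms or more after that restart is a recurrence. Grade 3 stays the stricter row, because it also reduces the dose.

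No separate recovery limit is needed. The section 6.5 rule on interruptions of more than 4 weeks caps the hold.

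The cost is a few extra ECGs and some missed doses for an affected patient. For an event at an on-schedule Day 15 visit, at most the seven cycle 1 doses of Days 15-21 are lost (ten if the visit is on Day 12, four if on Day 18). If QTcF did not recover in cycle 1, daily ECGs on Days 16-28 would number 13. The patient would also contribute less exposure to the cycle 1 DLT assessment, since section 6.6 counts anyone who started LEE011 and sets no minimum number of doses. That loss is acceptable against re-dosing unresolved prolongation, but it should be noted when the cohort is reviewed.
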